### ***Serious adverse events (SAEs)***

- Summary of SAEs after vaccination:
  - Within 7 days after vaccine injection
  - Within 28 days after vaccine injection
  - After vaccine injection during the whole study
- All and related SAEs by seriousness criterion
  - Within 28 days after vaccine injection
  - After vaccine injection during the whole study
- All and related SAEs by SOC and PT
  - Within 28 days after vaccine injection
  - After vaccine injection during the whole study
- All and related SAEs by outcome
  - Within 28 days after vaccine injection
  - After vaccine injection during the whole study

Listings of serious adverse events/reactions will be presented. SAEs not included in the safety analysis will be also presented in listings.

### ***AEs of Special Interest (AESIs)***

AESIs will be listed by each AESI as shown in [Table 7](#) separately.

#### **2.4.4.2 Deaths**

Listing of death will be presented.

#### **2.4.4.3 Analyses of laboratory variables**

Not applicable

#### **2.4.4.4 Analyses of vital sign variables**

Not applicable

#### **2.4.4.5 Analyses of body stature variables**

The summary statistics of all body statures variable at V1 will be presented as the result of demographics and baseline characteristics described in [Section 2.1.1](#) and [Section 2.4.1](#).

#### 2.4.4.6 Analyses of electrocardiogram variables

Not applicable

#### 2.4.5 Analyses of immunogenicity data

QIV-HD vaccine and QIV-SD vaccine contain the following strains:

	QIV-HD	QIV-SD
H1N1	A/Michigan/45/2015(H1N1)	A/Singapore/GP1908/2015(IVR-180)(H1N1)pdm09
H3N2	A/Hong Kong/4801/2014(X-263B)(H3N2)	A/Hong Kong/4801/2014(X-263)(H3N2)
B (Yamagata lineage)	B/Phuket/3073/2013	B/Phuket/3073/2013
B (Victoria lineage)	B/Brisbane/60/2008	B/Texas/2/2013

For the purposes of this section, the 7 virus strains in the vaccine groups will be labeled as follow:

- A/Michigan/45/2015(H1N1) A1
- A/Singapore/GP1908/2015(IVR-180)(H1N1)pdm09 A1-like
- A/Hong Kong/4801/2014(X-263B)(H3N2) A2
- A/Hong Kong/4801/2014(X-263)(H3N2) A2-like
- B/Phuket/3073/2013 B1
- B/Brisbane/60/2008 B2
- B/Texas/2/2013 B2-like

The immunogenicity analyses will be performed on the PPAS and the FAS. The main immunogenicity analyses will be conducted on Cohort 2 for the PPAS. Similar analyses with the main immunogenicity analyses will also be conducted on Cohort 2 for the FAS and Cohort 1+Cohort 2 for PPAS and FAS, unless otherwise specified.

For descriptive purposes, no hypothesis will be tested.

Assuming that  $\log_{10}$  transformation of the titers/data follows a normal distribution, at first, the mean and the 95% CI will be calculated on  $\log_{10}$  (titers/data) using the usual calculation for normal distribution (using Student's  $t$  distribution with  $n-1$  degree of freedom) as described in [Section 2.5.8.1](#) and [Section 2.5.8.2](#), then antilog transformations will be applied to the results of calculations, in order to provide GMs and their 95% CI.

For categorical data such as seroprotection and seroconversion, the percentage of subjects achieving the endpoint and the corresponding 95% CIs (Clopper-Pearson method) (2) will be performed for pre-vaccination (V1) and post-vaccination immunogenicity (V3) (See the detail in [Section 2.5.8.3](#)). The 95% CI of the difference in percentage between time points and vaccine

group will be computed using the Wilson score method without continuity correction, quoted by Newcombe (3) (See the detail in [Section 2.5.8.4](#)).

For GMTs of HAI, the following will be analyzed by vaccine groups and strains.

- GMTs of HAI for QIV-HDs and QIV-SD, and the ratio of GMTs of HAI for each QIV-HD/QIV-SD at V3 after vaccination
- GMTs of HAI for QIV-HDs and QIV-SD using strains selected for each vaccine, and the ratio of GMTs of HAI for each QIV-HD/QIV-SD at V3 after vaccination
- Ratio of GMTs of HAI for QIV-HDs between the 2 different administration routes at V3 after vaccination

GMTs of HAI for each vaccine group at V1 and V3 after vaccination and the corresponding ratio of GMT will be summarized by strains.

For seroconversion rates, the following will be analyzed by vaccine groups and strains.

- Seroconversion rates and the difference of each QIV-HD and QIV-SD (QIV-HD – QIV-SD) at V3 after vaccination
- Seroconversion rates using strains selected for each vaccine and the difference of each QIV-HD and QIV-SD (QIV-HD – QIV-SD) at V3 after vaccination
- Seroconversion rates and the difference of QIV-HDs between the 2 different administration routes at V3 after vaccination

For seroprotection rate, the following will be analyzed by vaccine groups and strains

- Seroprotection rates of HAI for QIV-HDs and QIV-SD at V3 after vaccination
- Seroprotection rates of HAI for each vaccine group at V1 and V3 after vaccination

Immunogenicity data will be analyzed using GMTs, seroconversion rate, and seroprotection rate at each time point by following subgroups:

- Age: 65-<75 and  $\geq 75$  years
- Sex: Male and Female
- Previous influenza vaccination status: Yes and No
- Baseline seropositivity status:  $<10$  [1/dil] and  $\geq 10$  [1/dil]

For comparison between groups in terms of GMTs, the exploratory analyses will be performed if necessary.

The followings will be presented as the summary of HA antibody response for each antigen:

- The number of subjects with HAI titer  $<10$  [1/dil] and  $\geq 10$  [1/dil], the number of subjects with seroprotection ( $\geq 40$  [1/dil]), and summary of titers [1/dil] (using geometric mean and the corresponding 95% CI, median, minimum and maximum value of antilog transformed value, and mean and standard deviation calculated on  $\log_{10}$  (titers/data)) at V1 and V3

- GMTR of the individual titers (using geometric mean and the corresponding 95% CI, median, minimum and maximum of antilog transformed value, and mean and standard deviation calculated on  $\log_{10}$  (titers/data)) at V3 over V1, and the number of subjects with seroconversion at V3

In addition, Reverse Cumulative Distribution Curve (RCDC) by vaccine groups and timepoints (V1 and V3) will be presented in a graph for each strain in Cohort 2 for the PPAS and FAS.

Individual diagram of titers will be also presented for each strain by vaccine groups in Cohort 2 for the PPAS.

To assess the immunogenicity of -like strains, the following results will be presented for corresponding strains by vaccine groups:

- GMTs of HAI at V1, V3 and GMTR of HAI for V3/V1 with the corresponding 95% CI
- Seroconversion rate
- Seroprotection rates at V1 and V3

Using the titer including all of the 3 vaccine groups and all of the 2 time points for a pair of -like strains, scatter plots with the titers of 2 -like strains will be presented, and the Pearson product-moment correlation coefficient  $r$  between -like strains will be calculated using  $\log_{10}$  transformed values of the titers in Cohort 2 for the PPAS and FAS. Also a regression line will be drawn and the coefficient of determination  $R^2$  will be calculated through a simple regression model using  $\log_{10}$  transformed values of the titers.

Individual immunogenicity data will be presented in listings.

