In this study, QIV-HD will be compared to a local QIV-SD, and it is possible that the two vaccines contain different strains based on comparison of strains between Sanofi Pasteur QIV-HD (based on WHO / VRBPAC recommendations) and a local QIV-SD (based on NIID). Sanofi Pasteur plans on performing the HAI testing using both the QIV-HD and QIV-SD strains as test antigens for all the subjects, irrespective of the vaccine received. For example, if QIV-HD is comprised of a, b, c and d strains and QIV-SD is comprised of a, b, c and “d-like” strains (3 common and 1 “-like strain”), the proposed testing strategy would require HAI testing of sera from all subjects (irrespective of the vaccine received) with a, b, c, d and “d-like” strain test antigens in order to evaluate the comparability between the “-like strains” in this study.

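### The -like strain correlation pools both visits and all three arms, so r and R² partly measure the vaccine response and barely register a moderate own-antigen advantage

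*SAP*

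**What the plan says.** SAP 2.4.5 lists seven antigens. B/Phuket is common to both vaccines. The H1N1, H3N2 and B/Victoria components each form a pair, with one member in QIV-HD and the other in QIV-SD. SAP 2.1.5 has every subject's serum tested against both members, "in order to evaluate the comparability between the “-like strains” in this study".

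For each pair, the end of SAP 2.4.5 specifies a scatter plot and a Pearson r on log10 titers in Cohort 2 (PPAS and FAS), "Using the titer including all of the 3 vaccine groups and all of the 2 time points for a pair of -like strains". R² "will be calculated through a simple regression model using" the same log10 titers. The model has no term for group, visit or subject, and no r by group or by visit is planned.

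The same section also plans by-group output:
- "To assess the immunogenicity of -like strains, the following results will be presented for corresponding strains by vaccine groups", including "GMTs of HAI at V1, V3 and GMTR of HAI for V3/V1 with the corresponding 95% CI", seroconversion, and seroprotection at both visits.
- "For GMTs of HAI, the following will be analyzed by vaccine groups and strains", including the QIV-HD/QIV-SD ratio at V3, and a version that uses the strains selected for each vaccine.
- Seroconversion differences by strain, and reverse cumulative distribution curves by group and visit.

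On testing, the section says: "For descriptive purposes, no hypothesis will be tested". No cut-off, CI or decision is attached to r or R².

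**The concern.** Vaccination is expected to raise titers to both members of a pair. When V1 and V3 sera share one scatter plot, the gap between the two clouds adds covariance that reflects the vaccine response rather than how closely the two antigens agree on sera taken at the same visit from the same arm. Pooling the arms adds a second problem. Each vaccine carries a different member of the pair, so the likely way for comparability to fail is that each vaccine favours its own antigen, and one overall r averages across that pattern.

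The scatter plot, r, line and R² are the only planned outputs that set a subject's two titers against each other. With no criterion stated, r will be read at face value. A high r could then be taken as evidence that the choice of test antigen does not matter to the QIV-HD/QIV-SD comparison for three of the four vaccine components.

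**Working it through.** **Inputs from the documents.** Three groups, two visits and 55 subjects per group in Cohort 2 (SAP 1.3), so up to 2 × 165 = 330 points from 165 subjects per pair. LLOQ is 10, and lower values are set to 5 (SAP 2.1.5 and 2.5.3.1). The documents give no SD, expected fold-rise, correlation or comparability criterion, so there is no planned figure to reproduce.

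**Assumptions.** Log10 SD within arm and visit, s, is 0.4 to 0.6. Correlation between the two antigens within arm and visit, ρ, is 0.5 to 0.9. V3/V1 fold-rise is 2 to 10 in each QIV-HD arm and 1.5 to 5 in QIV-SD. Baseline means are equal.

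**Formula.** Over the six equal arm-by-visit strata, with V_A, V_B and C_AB the variances and covariance of the stratum means on antigens A and B:

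pooled r = (ρs² + C_AB) / √[(s² + V_A)(s² + V_B)]

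**Step 1: same response to both antigens.** Take fold-rises 4/4/2 (QIV-HD IM, QIV-HD SC, QIV-SD). The stratum means relative to baseline are 0, 0, 0, 0.602, 0.602 and 0.301, so V_A = V_B = C_AB = 0.1359 − 0.0629 = 0.0730. With s = 0.5:
- ρ = 0.5: (0.125 + 0.073)/0.323 = 0.61; R² goes from 0.25 to 0.38
- ρ = 0.7: (0.175 + 0.073)/0.323 = 0.77; R² from 0.49 to 0.59
- ρ = 0.9: (0.225 + 0.073)/0.323 = 0.92; R² from 0.81 to 0.85

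Across the whole assumed range:

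| ρ | lowest pooled r (s 0.6, rises 2/2/1.5) | highest pooled r (s 0.4, rises 10/10/5) |
|---|---|---|
| 0.5 | 0.525 | 0.785 |
| 0.7 | 0.715 | 0.871 |
| 0.9 | 0.905 | 0.957 |

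The increase therefore runs from 0.905 − 0.9 = 0.005 to 0.785 − 0.5 = 0.285.

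**Step 2: own-antigen advantage f.** Let QIV-HD raise A by 4√f and B by 4/√f, and let QIV-SD raise A by 2/√f and B by 2√f. For f = 1.5 the fold-rises are 4.90 and 3.27 for QIV-HD, and 1.63 and 2.45 for QIV-SD. The QIV-HD/QIV-SD ratio is 4.90/1.63 = 3.0 on A and 3.27/2.45 = 1.33 on B. Then V_A = 0.0958, V_B = 0.0575 and C_AB = 0.0693. With s = 0.5 and ρ = 0.7:

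pooled r = 0.2443/√(0.3458 × 0.3075) = 0.75

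For f = 1, 1.5, 2, 3 and 4, pooled r is 0.77, 0.75, 0.72, 0.64 and 0.57. A moderate advantage hardly moves r. A strong one takes it below the within-stratum value of 0.7.

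**Step 3: simulation check.** 1,000 trials were run with 55 per arm, s = 0.5, ρ = 0.7, two-fold dilution steps, values below 10 set to 5, baseline GMT about 20 and V1–V3 correlation 0.5 (the last two assumed). Pooled r averaged 0.74 at f = 1 and 0.72 at f = 1.5. The average r within arm at V3 was 0.67 in both cases.

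**Step 4: what the by-group tables would show.** With n = 55 and s = 0.5, the 95% CI factor for a between-group GMT ratio is 10^(1.982 × 0.5 × √(2/55)) = 1.545. The two ratios become 3.0 (1.94 to 4.64) and 1.33 (0.86 to 2.06). The difference is visible, but the intervals overlap because neither uses the pairing within subject.

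**Step 5: the paired ratio.** At ρ = 0.7 the within-subject log10 difference has SD 0.5 × √(2 × 0.3) = 0.387, and its CI factor by group is 10^(2.005 × 0.387/√55) = 1.27. At f = 1.5 the A/B ratio is 1.5 (1.18 to 1.91) in a QIV-HD arm and 0.67 (0.52 to 0.85) in QIV-SD. In the simulation, the contrast of this ratio between the combined QIV-HD arms and QIV-SD detected f = 1.5 in at least 99% of trials for ρ of 0.5, 0.7 and 0.9.

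**The case against.** A reader might infer that the plan hides a vaccine-by-antigen difference. It does not. GMTs, fold-rises, seroconversion and QIV-HD/QIV-SD ratios are all reported by group and strain, so the 3.0 and 1.33 in step 2 are numbers the SAP would print. With complete pairs, the ratio of the two GMTs in a group is also the geometric mean of the within-subject ratio. That point estimate can be read from the planned tables, and only its paired CI is missing.

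A reader might also infer that pooling is bound to inflate r. That depends on inputs the documents do not give. If the antigens already agree closely, the change is small. This is plausible for the H3N2 pair, where both antigens carry the name A/Hong Kong/4801/2014. Under a strong own-antigen advantage r falls.

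Stratified r would not reveal the interaction either. A constant shift of one antigen within an arm leaves r unchanged, as the 0.67 in step 3 shows. This objection stands, and it is why the fix needs more than stratified correlations.

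Finally, agreement over the full titer range is a legitimate thing to plot, and the analysis is descriptive with nothing depending on r. Both points stand. They support keeping the pooled plot, but they do not make pooled r a good single summary of comparability.

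**Conclusion.** The point holds for r, the regression line and R², and no further. As planned, these mix agreement between antigens with the size of the vaccine response. The increase in r is about 0.01 to 0.29 over the assumed range, material when the within-stratum correlation is moderate and minor when it is near 0.9. A 1.5-fold own-antigen advantage changes pooled r by only 0.02. These sizes rest on assumed SDs, fold-rises and correlations; that pooled r depends on the vaccine response follows from the formula itself.

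The documents do not support the stronger readings that the interaction is lost from the plan or that a QIV-HD/QIV-SD comparison hinges on r. Only the H1N1, H3N2 and B/Victoria pairs are affected. The two points per subject are not independent, but no CI or test on r is planned, so this has little consequence. The change is a cheap improvement to a descriptive output.

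**What to change.** In SAP 2.4.5:
1. Present the scatter plot, regression line, r and R² by vaccine group and visit, at minimum V3 by group.
2. Keep the pooled plot and r as a summary labelled as pooled, with points marked by group and visit.
3. Add, for each pair, the within-subject log10 ratio of strain to -like strain at V3 by vaccine group, back-transformed, with a 95% CI.
4. State that any reading of a vaccine-by-antigen difference rests on that ratio and the by-group GMTs, not on r or R².

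The cost is a few more outputs from existing data, and about 55 subjects behind each r instead of up to 330 pooled points.

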### Immunogenicity

To describe the immune responses induced by each group (as assessed by HAI geometric mean titers [GMTs] and seroconversion rates) for the 4 common virus strains at 28 days post-vaccination.

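### The -like strain comparability analysis has no paired within-serum antigen ratio with a confidence interval, and r and R² hardly respond to a level shift

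*SAP*

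**What the plan says.** SAP 2.1.5 and Protocol 9.2.2 plan to titrate all sera, whichever vaccine was given, against the strains of both vaccines, using both sets of "test antigens in order to evaluate the comparability between the" -like strains. SAP 2.4.5 labels three of the four strain positions as -like pairs (H1N1, H3N2 and B Victoria). Only B Yamagata is identical in the two vaccines. The immunogenicity objective in SAP 1.2 nevertheless speaks of responses "for the 4 common virus strains at 28 days post-vaccination".

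For the -like strains, SAP 2.4.5 plans two sets of output:

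- By vaccine group, for each antigen: "GMTs of HAI at V1, V3 and GMTR of HAI for V3/V1 with the corresponding 95% CI", plus seroconversion and seroprotection rates.
- Pooled over groups and visits ("Using the titer including all of the 3 vaccine groups and all of the 2 time points for a pair of -like strains"), the two antigens of a pair are set against each other on the log10 scale: "scatter plots with the titers of 2 -like strains will be presented, and the Pearson product-moment correlation coefficient". A further item is worded "Also a regression line will be drawn and the coefficient of determination", meaning R² from a simple linear fit.

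The same section also compares the vaccines with each read on its own strain: "GMTs of HAI for QIV-HDs and QIV-SD using strains selected for each vaccine, and the ratio of GMTs of HAI for each QIV-HD/QIV-SD", and "Seroconversion rates using strains selected for each vaccine and the difference of each QIV-HD and QIV-SD". The corresponding contrasts on a common antigen are planned beside them.

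**The concern.** Comparability of two test antigens includes whether they give the same titer on the same serum. Correlation does not address this. If one antigen reads twice as high as the other throughout, log10 titers move by a constant and r is unchanged in principle.

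The other planned outputs help only in part. Two antigen GMTs can be divided to get the point value of the shift, but both come from the same sera, so their separate CIs do not give the precision of the ratio. Every ratio or difference listed in SAP 2.4.5 is between vaccine groups, between routes, or between visits within one antigen. None is antigen over antigen within a serum.

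The own-strain contrasts are where this matters. They put QIV-HD on one antigen against QIV-SD on another, so any difference between the antigens enters the result. The factor linking the own-strain ratio to the same-antigen ratio is not reported with a CI.

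**Working it through.** The plan states no comparability criterion, expected offset or titer SD, so there is no figure of its own to reproduce. From the documents: 55 subjects per group in Cohort 2 (SAP 1.3), hence 3 × 55 = 165 sera per visit and 330 pooled points; at most 5% missing (Protocol 12.3.2), hence 165 × 0.95 ≈ 157; titers below 10 set to LLOQ/2 = 5 (SAP 2.5.3.1). All titer parameters below are assumptions.

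**1. r and a constant shift.** For log10 titers x and y, corr(x, y + c) = corr(x, y). Only the LLOQ rule and the dilution steps disturb this. Simulation: 3 × 55 subjects with no vaccine difference; log10 baseline mean log10(10), log10(20) or log10(40), SD 0.45; log10 rise mean 0.6, SD 0.4, floored at 0; two reads with noise SD 0.12, cut to two-fold dilutions from 1:10. Results at baseline mean 20:

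| Offset | r, no antigen-specific scatter | r, between-antigen difference SD 0.2 |
|---|---|---|
| 1 | 0.970 | 0.920 |
| 1.25 | 0.970 | 0.919 |
| 2 | 0.966 | 0.916 |

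The largest fall in any setting was 0.010. The 0.2 is the SD of the difference between antigens; applied to each antigen separately it gives r of about 0.877, still nearly flat across offsets.

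**2. Precision of a paired ratio.** The 95% CI factor is 10^(t(n−1) × SDdiff / √n), with SDdiff assumed at 0.15 to 0.30:

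- n = 165: ×/÷ 1.05 to 1.11
- n = 157: ×/÷ 1.06 to 1.12
- n = 55: ×/÷ 1.10 to 1.21

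For one antigen's GMT in a group of 55, 10^(t(54) × SD / √55) with SD 0.4 to 0.6 gives ×/÷ 1.28 to 1.45. A 1.25-fold shift therefore leaves the two separate CIs overlapping, while the paired CI in one group has a lower limit of 1.25 / 1.21 = 1.03 or higher. Treating the two GMTs as independent, with the formula of SAP 2.5.8.2 and SD 0.5, gives ×/÷ 1.55.

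**3. Link to the own-strain contrast.** With A the HD strain and A′ the SD strain, on log10 titers at V3:

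mean_HD(A) − mean_SD(A′) = [mean_HD(A) − mean_SD(A)] + mean_SD(A − A′).

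So the own-strain GMT ratio equals the same-antigen ratio times the within-serum antigen ratio in the QIV-SD group. This is exact when each serum has both results, as in the PPAS if SAP 2.3.2 is read as requiring a valid V3 result on every strain.

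**4. Size of the carry-over.** Same simulation, HD antigen reading higher, with 55%, 30% or 12% of baselines below 10:

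- 2-fold offset: own-strain GMT ratio about 1.91, 1.97, 1.98; seroconversion difference about +10, +6, +2 percentage points.
- 1.25-fold offset: own-strain GMT ratio 1.22 to 1.25; seroconversion difference from about +4 down to about +1 point.

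If the SD antigen reads higher, the directions reverse.

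**5. Limit of the remedy.** Setting titers below 10 to 5 shrinks the ratio where many titers are low. A true 2-fold offset reads as 1.67, 1.87 and 1.96 at V1 for the same three baselines, and as 1.92, 1.97 and 1.99 at V3.

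**The case against.** A reader might infer that nothing planned can show a level shift, the regression line included. The documents do not support that. A least-squares line passes through both means, so its height at mean x, less mean x, is exactly the mean paired log10 difference. Its intercept is not the shift, but the SAP does not list the intercept as an output, so that cannot be held against the plan. Scatter plots, per-antigen GMTs with CIs, reverse cumulative curves and individual listings also let a shift be seen.

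A reader might also infer that the vaccine comparison is compromised. It is not. The same-antigen GMT ratios and seroconversion differences contain no cross-antigen shift, are planned with CIs (SAP 2.5.8.2 and 2.5.8.4), and sit beside the own-strain versions. No hypothesis is tested.

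Two further objections have force. Comparability is not defined in either document, so reading it as agreement in level is reasonable but is not a stated criterion. And the V3 ratio in the QIV-SD group is not a pure assay difference: those subjects received the SD strain, so it includes genuine homologous response.

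What stands is narrower: r and R² are nearly blind to a shift, and the one paired quantity that measures it has no planned estimate with a CI.

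**Conclusion.** The point holds as a cheap improvement. That the paired ratio with a CI is absent is clear from SAP 2.4.5, and that r hardly responds to a shift follows from algebra and survives the LLOQ rule in simulation.

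The consequence is much less certain. The documents give no offset. It may be small, notably for H3N2, where both vaccines carry A/Hong Kong/4801/2014 and differ only in the X-263B and X-263 designations. The figure of about 1.9 to 2.0 for the own-strain GMT ratio rests on a chosen 2-fold offset and assumed titers; at 1.25-fold the effect is about 1.2 on the GMT ratio and roughly 1 to 4 points on seroconversion. A shift large enough to mislead is a possibility that the planned output would not quantify with its uncertainty; the documents do not show that one exists.

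**What to change.** For each of the three -like pairs in Cohort 2, on the PPAS and FAS, report beside r and R² the geometric mean within-serum ratio of the two antigens with a 95% CI. Apply the formula in SAP 2.5.8.1 to the paired log10 differences: on all sera at V1, and by vaccine group at V3. Show the number of sera below 10 on both antigens.

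Add one sentence to the own-strain GMT and seroconversion items in SAP 2.4.5: these contrasts combine the vaccine effect with any difference between the antigens, which at V3 includes both assay level and strain-specific (homologous) response, and should be read with the within-serum ratio and the same-antigen contrasts.

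Note with the table that the V1 ratio avoids the vaccine response, but is pulled towards 1 by the LLOQ/2 rule when many baselines are below 10 and may reflect past exposure to one strain.

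The cost is one small table per pair and one sentence. No new sample, assay, test or CI method is needed, and nothing planned is removed.
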